## 7.0 TRIAL PROCEDURES

[Table 6.1, Schedule of Assessments – Study Flow Chart](#), summarizes the frequency and timing of study activities and assessments from Screening through the end of the study and Post-treatment Visits (30-Day Safety Follow-up (SFU) Visit and monitoring for overall survival). Visits should occur as scheduled in Table 6.1 to the extent possible.

### 7.1 Visit Windows

All treatment visits should occur on the visit days specified in [Table 6.1, Schedule of Assessments](#). However the following visit windows, while not desirable, are acceptable:

- For study medication administration, a visit window of +/- 3 days
- For hematology and chemistry laboratories, a visit window of - 3 days
- For imaging, a visit window of +/- 7 days (which should follow calendar days and not be adjusted for cycle delays)
- For the End of Study Visit, a visit window of +3 days
- For the 30-Day SFU Visit, a visit window of -7 days
- For Every-2-Month Survival Monitoring, a visit window of +/- 7 days

### 7.2 Screening Period

Prior to any study-specific assessments or Screening procedures, a written, signed ICF will be obtained from subjects. A copy of the signed ICF will be provided to the subject.

A Screening examination should be performed between 1 and 30 days before the first day of treatment to determine study eligibility. Subjects who meet all entry criteria will be enrolled into the study.

A Screen Failure Log must be maintained by the Investigator for all screened subjects.

A subject may be re-screened an additional 2 times if entry criteria are not met, as long as this occurs within 90 days of the signing of the ICF.

### 7.3 Treatment Period (Treatment Cycles)

Study Day 1 is defined as the day of the first dose of study medication.

The study treatment period will be divided into treatment cycles. Each cycle will be 3 weeks in duration and defined by the frequency of pembrolizumab administration. During each cycle, subjects will dose weekly with Imprime PGG for all 3 weeks (Days 1, 8, and 15). Pembrolizumab will be dosed on D1 of each 3-week cycle. Subjects will be dosed until

disease progression or death or study termination or 2 years or until any of the criteria for study drug discontinuation are met (whichever occurs first).

See [Section 5.2.2 Timing of Dose Administration](#) for the order in which the study medications must be administered.

### 7.3.1 Clinical Assessments and Procedures

### 7.3.2 Tumor Response Criteria

Tumour response will be evaluated according to the RECIST v1.1 (see [Appendix 14.5](#)) (<http://www.eortc.be/Recist/documents/RECISTGuidelines.pdf>) and clinical criteria (Eisenhauer et al, 2009). Disease progression will be defined as per RECIST version 1.1 guidelines on radiological, clinical, or symptomatic progression.

Evaluation of response by RECIST v1.1 criteria should be performed at baseline and then at 6-week intervals beginning at Week 6. Immune-related response criteria (irRECIST) (see [Appendix 14.6](#)) may be used for clinical management of subjects, but will not be used for OR evaluation (other than as an exploratory endpoint). Therefore RECIST 1.1 will be adapted to account for the unique tumor response characteristics seen with immunotherapy treatment. Immunotherapeutic agents such as pembrolizumab may produce antitumor effects by potentiating endogenous cancer-specific immune responses. The response patterns seen with such an approach may extend beyond the typical time course of responses seen with cytotoxic agents, and can manifest a clinical response after an initial increase in tumor burden or even the appearance of new lesions. Standard RECIST may not provide an accurate response assessment of immunotherapeutic agents such as pembrolizumab. Therefore, RECIST 1.1 will be used with the following adaptations:

If radiologic imaging verifies initial PD, tumor assessment should be repeated  $\geq 4$  weeks later in order to confirm PD with the option of continuing treatment per the conditions stated below, while awaiting radiologic confirmation of progression.

If repeat imaging shows  $< 20\%$  or  $< 5$  mm absolute increase in tumor burden compared to nadir, stable or improved previous new lesion (if identified as cause for initial PD), and stable/improved non-target disease (if identified as cause for initial PD), treatment may be continued / resumed.

If repeat imaging confirms PD due to any of the scenarios listed below, subjects will be discontinued from study treatment\*.

In determining whether or not the tumor burden has increased or decreased, the Investigator should consider all target lesions as well as non-target lesions.

Scenarios where PD is confirmed at repeat imaging:

- Tumor burden remains  $\geq 20\%$  and at least 5 mm absolute increase compared to nadir

- Non-target disease resulting in initial PD is worse (qualitative)
- New lesion resulting in initial PD is worse (qualitative)
- Additional new lesion(s) since last evaluation

In subjects who have initial evidence of radiological PD, it is at the discretion of the subject and the Investigator whether to continue a subject on study treatment until repeat imaging is obtained:

- The subject must re-consent to the study, in order to continue receiving study medication in light of the radiological evidence of PD.
- The Investigator's clinical judgment decision regarding the subject continuing should be based on the subject's overall clinical condition, including performance status, clinical symptoms, and laboratory data.

Subjects may receive study treatment while waiting for confirmation of PD if they have re-consented and are clinically stable as defined by the following criteria:

- Absence of signs and symptoms indicating disease progression
- No decline in ECOG performance status
- Absence of rapid progression of disease
- Absence of progressive tumor at critical anatomical sites (eg, cord compression) requiring urgent alternative medical intervention

When feasible, subjects should not be discontinued until PD has been confirmed. This allowance to continue treatment despite initial radiologic progression takes into account the observation that some subjects can have a transient tumor flare in the first few months after the start of immunotherapy, but with subsequent disease response. Subjects that are deemed clinically unstable are not required to have repeat imaging for confirmation of progressive disease.

**\*Note:** If PD is confirmed but the subject is experiencing an extraordinary clinical benefit, contact Sponsor to discuss continuing treatment.

All RECIST assessments (v1.1 or irRECIST) will be evaluated against the initial lesion measurement values from the baseline computed tomography (CT) scan or magnetic resonance imaging (MRI) obtained prior to the initiation of study treatment. Either CT or MRI is acceptable, but the same method must be used throughout the study for any individual subject. If MRIs are used, they must include images of the head, chest, abdomen, and pelvis.

### **7.3.3 Tumor Imaging**

Tumor imaging should be performed by CT (preferred). MRI should only be used when CT is contraindicated or for imaging in the brain, but the same imaging technique should be used in a subject throughout the trial. A CT scan is the more commonly used modality and is preferred for the majority of subjects. An MRI can be utilized if clinically appropriate.

Imaging should include the chest, abdomen, and pelvis.

For TNBC subjects, bone scans will also be utilized to assess osseous metastases. Additionally, X-ray evaluation will be obtained for symptomatic sites with negative bone scan evaluations. The sponsor should be notified of any supplemental imaging done to support a positive or negative bone scan.

#### **7.3.3.1 Initial Tumor Imaging**

Initial tumor imaging at Screening must be performed within 28 days prior to the date of first dose of trial treatment. The Investigator must review screening images to confirm the subject has measurable disease per RECIST v1.1.

Scans performed as part of routine clinical management are acceptable for use as initial tumor imaging if they are of diagnostic quality and performed within 28 days prior to the start of study treatment and viewed by the Investigator.

#### **7.3.3.2 On Study Tumor Imaging**

The first on study imaging assessment should be performed 6 weeks ( $\pm 7$  days) from the date of first dose of trial treatment. Subsequent tumor imaging should be performed every 6 weeks ( $\pm 7$  days) or more frequently if clinically indicated. Imaging should not be delayed for delays in cycle starts or extension of study medication cycle intervals.

Per RECIST v1.1, partial or complete response should be confirmed by a repeat tumor imaging assessment not less than 4 weeks from the date the response was first documented. The tumor imaging for confirmation of response may be performed at the earliest 4 weeks after the first indication of response, or at the next scheduled scan (ie 6 weeks later), whichever is clinically indicated.

Continue to perform imaging until whichever of the following occurs first:

- Disease progression
- The start of new anti-cancer treatment
- Withdrawal of consent
- Death
- End of the study

### **7.3.4 RECIST Assessment of Disease**

RECIST v1.1 will be applied by the Investigator as the primary measure for assessment of tumor response, date of disease progression, and as a basis for all protocol guidelines related to disease status.

irRECIST will be applied by the Investigator solely for clinical management of subjects, as described in [Section 7.3.2](#) and in [Appendix 14.6](#).

### **7.3.5 Tumor Biopsy Samples**

Tumor biopsy information must be collected for this study as follows:

1. An official diagnostic pathology report +/- archival tumor biopsy sample (in order to be eligible for the study)

An additional 3 tumor biopsy samples, preferably obtained from the same localized region, are highly desirable when feasible and are as follows:

2. Sample before the first dose of study treatment (which will also be used for PD-L1 biomarker analysis)
3. Sample after Cycle 2 is completed but before initiation of Cycle 3 dosing (which will also be used for PD-L1 biomarker analysis)
4. Sample either at the time of response or at the End of Study Visit (if no response).

Note that for Sample 2 and Sample 3, the following condition must be met:

- The tumor tissue sample for PD-L1 biomarker analysis should be from a newly obtained core or excisional biopsy. Repeat samples may be required if adequate tissue is not provided. If submitting unstained cut slides, freshly cut slides should be submitted to the testing laboratory within 14 days from when the slides are cut.
- Submission of formalin-fixed paraffin embedded tumor tissue sample blocks are preferred; if submitting unstained slides, the slides should be freshly cut and submitted to the testing laboratory within 14 days from site slide sectioning date, otherwise a new specimen will be requested.

### **7.3.6 Physical Examination and Measurement of Vital Signs**

Vital signs will be measured on all subjects at Screening.

Subjects will undergo a complete physical examination (including observable tumor measurements) at the Screening and at the End of Study Visits.

Weight will be taken at Screening, on Day 1 of every 3-week treatment cycle before study drug is administered, and at the End of Study Visit.

### **7.3.7 Performance Status**

Performance status will be measured using the ECOG performance status scale (see [Appendix 14.3](#)). It is recommended, whenever that the subject be assessed by the same person throughout the study.

Performance status will be assessed at Screening, on Day 1 of every 3-week treatment cycle before study drug is administered, at the End of Study visit, and at the 30-Day Safety Follow-up (SFU) visit.

### **7.3.8 Clinical Safety Assessments**

The NCI CTC-AE version 4.03 will be used to evaluate the clinical safety of the treatment in this study. Subjects will be assessed for AEs at each clinical visit and as necessary throughout the study.

### **7.3.9 Planned DNA and RNA Analysis**

Understanding genetic determinants of drug response is an important endeavor during medical research. This research will evaluate whether genetic variation within a clinical trial population correlates with response to the treatment(s) under evaluation. If genetic variation is found to predict efficacy or adverse events, the data might inform optimal use of therapies in the patient population. This research contributes to understanding genetic determinants of efficacy and safety associated with the treatments in this study.

In addition to studying variation across the human genome, RNA expression profiles may be investigated.

### **7.3.10 Laboratory Assessments**

Laboratory safety assessments will be performed at the timepoints specified in [Section 6.1 Schedule of Assessments](#). All laboratory testing will be conducted via local laboratories. Normal ranges for the study laboratory parameters must be supplied to Biothera before study start by each investigational site.

Samples for PBMC, RNA, DNA, Serum ABA, Serum Cytokines, Serum Complement and inflammation markers, and potentially other serum proteins, will be collected by the central laboratory for conduct of the assays.

Please refer to [Table 3](#) below for the analytes to be collected in this study:

**Table 3. Laboratory Tests**

Hematology	Chemistry	Urinalysis	Other
Hematocrit	Albumin	Blood	Serum $\beta$ -human chorionic gonadotropin†
Hemoglobin	Alkaline phosphatase	Glucose	( $\beta$ -hCG)†
Platelet count	Alanine aminotransferase (ALT)	Protein	PT (INR)
WBC (total and differential)	Aspartate aminotransferase (AST)	Specific gravity	aPTT
Red Blood Cell Count	Lactate dehydrogenase (LDH)	Microscopic exam ( If abnormal results noted )	PK
Absolute Neutrophil Count	Carbon Dioxide ‡ ( $CO_2$ or bicarbonate)	Urine pregnancy test †	PBMC
	Uric Acid		Serum ABA
	Calcium		Serum Cytokines
	Chloride		RNA
	Glucose		PD-L1
	Phosphorus		DNA
	Potassium		Serum complement and inflammation markers
	Sodium		
	Magnesium		
	Total Bilirubin		
	Direct Bilirubin ( If total bilirubin is elevated above ULN )		
	Total protein		
	Blood Urea Nitrogen		
	Thyroid Function Panel		
	
 
• Total triiodothyronine (T3) or (FT3)
 
• Free thyroxine (FT4)
 
• Thyroid stimulating hormone (TSH)
 
		

† Perform on women of childbearing potential only. If urine pregnancy results cannot be confirmed as negative, a serum pregnancy test will be required.

‡ If considered standard of care in your region.

### 7.3.11 Pharmacokinetic Evaluations

Samples for sparse PK will be taken at specified times (please refer to [Table 4](#)) for all subjects on Cycle 1/Day 1 and on Cycle 3/Day 1.

See [Section 5.2.2 Timing of Dose Administration](#) for the order in which the study medications must be administered.

**Table 4. Time and Events for Sparse PK Collection**

Time (Hours)	All Subjects	
	Cycle 1/Day 1	Cycle 3/Day 1
Imprime PGG Infusion		
Pre-dose	X	X
0		
1.5 hrs ( $\pm 30$ min) post end of Imprime infusion	X	X
Pembrolizumab Infusion		
Pre-dose	X	X
0		
3 hrs ( $\pm 30$ min) post end of pembrolizumab infusion	X	X

### 7.3.12 Unscheduled Visits

Additional visits may be scheduled per the Investigator discretion if the subject's medical condition warrants, ensuring his/her safety and well-being. Any additional visits, examinations, or procedures must be documented.

## 7.4 Post-treatment Assessments

### 7.4.1 End of Treatment/End of Study Visit

Study drug will be discontinued upon disease progression, development of study withdrawal criteria, duration of 2 years in the study, or study closure. Subjects deriving clinical benefit from the administration of Imprime PGG + pembrolizumab and who have completed 2 years of study treatment may be candidates for continued treatment after discussion between the subject, Investigator, and Sponsor.

The End of Treatment Visit (EOT) should occur as soon as possible after the end of the cycle in which the last administration of study drug occurred (window of +3 days). During this visit, the following assessments will occur:

- ECOG Performance Status Score
- Physical examination
- Weight
- Adverse events recording
- Concomitant medications recording
- Hematology
- CBC/Differential\*
- RNA/DNA\*
- Chemistry
- Serum ABA\*
- Serum cytokines, serum complement, and inflammation markers\*
- If feasible, the fourth and final biopsy sample (unless it was collected earlier at time of response or progression)

\* Only collected once (instead of at both Pre-infusion and Post-infusion as at other visits as no study medication is administered at this visit)

#### **7.4.2 30-Day Safety Follow-up Visit (30-Day SFU)**

The 30-Day SFU visit will occur within 4 weeks (window of -7 days) of study drug dosing being stopped. During this visit, the following assessments will occur:

- ECOG Performance Status Score
- Pregnancy test for women of childbearing potential
- Adverse event recording
- Concomitant medications recording
- Hematology
- Chemistry

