### **7.4.3 Every 2-Month Overall Survival Monitoring**

Upon completion of the 30-Day SFU visit, subjects will be monitored on an every 2-month visit schedule for survival until death or until study completion. Study completion is defined as the death of at least 70% of subjects or 3 years after the last subject's first dose, whichever occurs earlier.

Only survival status and start of any new anti-cancer therapy will be collected during this period.

Subjects who discontinue study drug without evidence of PD per RECIST v1.1 will have CT scans or MRI every 6 weeks during the survival-monitoring period to determine disease status until PD.

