#### **8.1.2 Reporting and Treating Non-serious Adverse Events**

It is the responsibility of the Investigator to perform regular assessments for AEs. Subjects will be regularly queried about the occurrence of any AEs and will be monitored throughout the study for reactions to study drug and/or study procedures. The Investigator and clinical staff will record all AEs, whether volunteered by or elicited from the subject, at anytime

during a subject's participation in the study. All events occurring prior to the first dosing will be recorded on the Medical History eCRF, except an SAE leading to exclusion from the trial or as a result of a protocol-specified intervention as described in Section 8.2.2, will be recorded on the Adverse Event eCRF. All AEs occurring at any time after the initiation of the first dose of study drug up to 30 days following the last dose of study drug will be recorded on the Adverse Event eCRF. Adverse events will be recorded according to the CTCAE v4.03 (Appendix 14.4). Adverse events meeting the definition of SAE require additional reporting as described in the following section.

All subjects experiencing an AE will be evaluated by the Investigator and monitored until resolution of the event or until the Investigator deems the event clinically stable and/or at an acceptable level. Unless the event requires hospitalization (SAE), medical treatment will be provided to the subjects at the unit, and treatment medication and/or medical procedures will preferably be provided under the guidance of the treating-Investigator's clinical discretion. All AEs, including clinically significant laboratory abnormalities, will be followed until resolution. Serious adverse events require special reporting in addition to documentation in the eCRF as described in the section on Serious Adverse Events.

It is the Investigator's responsibility to provide his/her assessment of the relationship of the event to the study drug and the severity of the event using the following scales:

- Relationship
  - No (unrelated, not related, no relation) – The time course between the administration of study drug and the occurrence or worsening of the AE rules out a causal relationship and another cause (concomitant drugs, therapies, complications, etc.) is suspected

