12.2 Adverse Events

All subjects will be assessed regularly for the potential occurrence of adverse events (AEs) from the date of informed consent to 30 days after the last dose of study drug. The incidence of treatment-emergent AEs (TEAEs) will be summarized and tabulated using MedDRA (version 18.1), by System Organ Class (SOC) and Preferred Term (PT). A TEAE is defined as an AE that first occurs or worsens in severity on or after the first dose of any study drug and within 30 days after the last dose of any study drug.

The National Cancer Institute Common Terminology Criteria for Adverse Events (CTCAE) (Version 4.03) will be used to grade both clinical and laboratory AEs. A subject with several occurrences of the same AE will be counted once and classified by the most severe occurrence. AEs with missing severity ratings will be classified as having unknown severity.

An overview summary of AEs will be produced, which will include counts and percentages of subjects with any AEs and Grade III/IV AEs, AEs and Grade III/IV AEs related to study treatment, SAEs, SAEs related to study treatment, fatal SAEs, infusion reactions, AEs leading to dose delayed, dose reduced, and dose withdrawn for Imprime PGG, AEs leading to dose delayed and dose withdrawn for pembrolizumab, and AEs leading to study treatment discontinuation. AEs related to study treatment will be further categorized as AEs related to Imprime PGG and/or pembrolizumab, Imprime PGG only, pembrolizumab only, and both Imprime PGG and pembrolizumab.

A treatment-related AE is defined as an AE for which the investigator classifies the relationship to study treatment as “Yes”. A worst-case scenario approach will be taken to handle missing data, i.e. AEs related to study treatment will include events with the relationship to study treatment as ‘YES’ or missing. Adverse event data will be reviewed periodically to identify infusion reactions, new cancers, and events related to pembrolizumab overdose ($\geq 1000\text{mg}$).

The AE summary tables will use the following algorithms for counting subjects:

- **Preferred term rows:** each subject is counted once within each unique preferred term at the maximum grade. For example, if a subject has two headaches, the subject is counted only once under the preferred term “Headache”. Subjects experiencing the same AE preferred term several times with different grades will only be counted once with the maximum grade.

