12.3 Serious Adverse Events

Serious adverse events will be summarized similarly as AEs. A treatment related SAE is defined as an AE for which the investigator classifies the relationship to study drug as “Yes”. A worst- case scenario approach will be taken to handle missing data, i.e. SAEs related to study treatment will include events with the relationship to study treatment as ‘YES’ or missing.

For serious adverse events, the treatment-emergent time period begins at treatment enrollment through 90 days following cessation of treatment, or 30 days following cessation of treatment if the subject initiates new anticancer therapy, whichever is earlier.

Supportive listings with subject-level details will be generated for fatal and all SAEs separately.

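### Measured from the last dose, the 30-day safety follow-up visit falls before the 30-day adverse-event window closes, and no later contact is scheduled to ask about adverse events

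*Protocol*

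**What the plan says.** Protocol Section 7.4.2 sets the visit: "The 30-Day SFU visit will occur within 4 weeks (window of -7 days) of study drug dosing being stopped". Section 7.1 repeats the one-sided allowance ("For the 30-Day SFU Visit, a visit window of -7 days") and gives no plus side.

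The windows for counting events run longer:

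- **All adverse events.** Under Section 8.1.2, events "up to 30 days following the last dose of study drug will be recorded on the Adverse Event eCRF". SAP Section 12.2 defines treatment-emergent events on the same limit, "within 30 days after the last dose of any study drug", and says subjects are assessed regularly over that whole period.
- **Serious adverse events.** Protocol Section 8.2.2 and SAP Section 12.3 run the period "through 90 days following cessation of treatment, or 30 days following cessation of treatment if the subject initiates new anticancer therapy", whichever is earlier.

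After the visit, Section 7.4.3 moves subjects to two-monthly survival monitoring and says: "Only survival status and start of any new anti-cancer therapy will be collected during this period". The one addition is that subjects who stopped drug without progression "will have CT scans or MRI every 6 weeks during the survival-monitoring period to determine disease status until PD". No adverse-event question is attached to those scans. In the Section 6.1 flow chart, adverse-event monitoring ends at the 30-day visit and the post-treatment column carries survival monitoring only.

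The other visit after treatment that records adverse events is End of Treatment (EOT). Section 7.4.1 places it at the end of the cycle containing the last dose, with 3 days' grace.

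**The concern.** A safety follow-up visit normally closes the period over which events are counted. This one is named for Day 30 but timed to happen sooner, and nothing scheduled afterwards asks the question again. Safety is a primary objective, and the SAP's tables count events to 30 days and serious events to as long as 90. Protocol Section 5.2.1.2.2 itself warns that immune-related events can appear months after the last pembrolizumab dose.

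If late events surface only when a subject or outside physician volunteers them, the tables may understate them, and capture may differ between the roughly 25 planned sites. There is also a practical clash: for some subjects the follow-up visit can land on or before the EOT visit that it is meant to follow.

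**Working it through.** The documents give no figure to reproduce. The check is calendar arithmetic, with Day 0 as the date of the last dose.

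**1. Timing of the visit (Sections 7.4.2 and 7.1).** Latest: 4 × 7 = Day 28. Earliest: 28 − 7 = Day 21.

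**2. Adverse-event window (Section 8.1.2, SAP 12.2), closing at Day 30.** Days after the visit: 30 − 28 = 2, up to 30 − 21 = 9. That is 2/30 = 7% to 9/30 = 30% of the window.

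**3. Serious-event window (Section 8.2.2, SAP 12.3).** With no new therapy it closes at Day 90: 90 − 28 = 62, up to 90 − 21 = 69 days, or 69% to 77% of the window. If new anticancer therapy starts, the window closes at Day 30 and the remainder is 2 to 9 days.

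**4. Does EOT close the gap?** Imprime PGG is given on Days 1, 8 and 15 of a 21-day cycle. Taking the cycle end as Day 22, EOT falls at (22 − day of last dose) to that figure + 3:

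| Last dose on cycle day | EOT, days after last dose | Follow-up visit, days after last dose |
|---|---|---|
| 1 | 21–24 | 21–28 |
| 8 | 14–17 | 21–28 |
| 15 | 7–10 | 21–28 |

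EOT never reaches Day 30. After a Day 1 last dose the two ranges overlap, so the follow-up visit can coincide with EOT or precede it. After a Day 8 last dose they are at least 21 − 17 = 4 days apart.

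**5. Sensitivity to how the visit is read.**

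- *Nominal Day 30, following the visit's name, −7 days:* visit at Day 23 to 30. Adverse-event gap 0 to 7 days; serious-event gap 90 − 30 = 60 to 90 − 23 = 67 days.
- *Clock starts at a decision to stop, L days after the last dose:* visit at Day 21 + L to 28 + L. The latest visit reaches Day 30 once L is 2, and the earliest once L is 9. For illustration, assume L = 21, the 3-week limit on dosing delays and interruptions. The visit is then at Day 42 to 49 and 90 − 49 = 41 to 90 − 42 = 48 days of the serious-event window remain.

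The adverse-event gap therefore depends on the anchor. The serious-event gap remains in each case shown for subjects without new therapy.

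**6. Would the existing first survival contact cover Day 90?** Suppose the follow-up visit were moved to Day 30. Two months later (2 × 30.4375 = 61 days, using the SAP's month), less the 7 days that Section 7.1 allows, gives 30 + 61 − 7 = Day 84. That is before Day 90, so the contact needs its own lower limit.

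**The case against.** The best defence is that the plan relies on event-driven reporting, which does not end at the visit. Section 8.1.2 requires events to be recorded to Day 30 whether volunteered or elicited. Section 8.2.2 requires every serious event in its window to be reported within 24 hours, and related serious events at any time. Section 5.8.1 asks for reasonable efforts to monitor events after discontinuation, and unscheduled visits are allowed. All of this stands. A reader might infer that collection stops at the follow-up visit; the documents do not say so. Only the scheduled questioning stops.

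Three other strong readings are also unsupported.

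- **That the visit always precedes Day 30.** This holds from the last dose. Section 7.4.2 counts from when dosing is stopped, a term the protocol does not define, and a later decision date could carry the visit past Day 30.
- **That the SAP treats 30 and 90 days as observed time for every subject.** SAP Sections 12.2 and 12.3 say which events count as treatment-emergent. The tables are counts and percentages of subjects, with no person-time denominator.
- **That 62 to 69 days go unasked for everyone.** The serious-event window shortens to 30 days when new therapy starts, and death also ends it early. The documents do not say how many subjects this covers.

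It is also fair to say that the overlap with EOT arises after a Day 1 last dose, not generally, and that a visit held at exactly 4 weeks leaves only 2 adverse-event days. None of this supplies a scheduled question for the end of either window.

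**Conclusion.** The point holds as a gap in scheduled ascertainment. Taking the last dose as the anchor, 2 to 9 days of the 30-day adverse-event window follow the last scheduled question (0 to 7 on the nominal Day 30 reading). So do up to 62 to 69 days of the 90-day serious-event window in subjects who do not start new anticancer therapy.

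These are shares of time, not of events. The documents give no rate for late events, so under-counting is possible but its size cannot be stated. The response-rate analysis is unaffected. So is the Stage 1 safety rule, which uses Cycle 1 events and Cycle 2 recurrence of infusion reactions. The correction is inexpensive and bears on a primary objective, so it should be made.

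**What to change.** - **Sections 7.1 and 7.4.2.** Set the safety follow-up visit at 30 days after the last dose of either study drug, with a plus-only window, for example +7 days. This defines the anchor, puts the visit at or beyond the end of the adverse-event window, and places it after EOT (at most Day 24).
- **Sections 7.4.3 and 6.1.** Specify the first survival contact as on or after Day 90, overriding the minus side of the ±7-day allowance. Have it also ask about serious events from the follow-up visit to Day 90. For subjects who started new anticancer therapy the window ends at Day 30, which the moved visit already covers. Amend the sentence limiting what survival contacts collect.
- **Subjects already past this point.** State in the SAP and the study report that adverse-event follow-up after the visit was unscheduled.

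The cost is protocol wording and one question at an existing contact, with no new visit. The downside is a slightly later follow-up visit, which some subjects may reach after starting new therapy; that start date is collected anyway. Non-serious events first arising after Day 30 would remain outside collection, as the protocol intends.
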